During the Follow-up Period, long-term safety, survival status, disease progression, subsequent anticancer therapy, and occurrence of other primary malignancy data will be collected as well as ADA sampling if applicable. During the Follow-up Period, subjects should be followed for safety up to 30 days after the last dose of ibrutinib or 100 days after the last nivolumab infusion, whichever is later. The safety includes adverse event reporting and laboratory assessments (at the first follow up). Thereafter, follow-up visits will be completed approximately every 3 months until death or the end of study. Subjects who have developed treatment-related Grade 3 or higher toxicity at the end of treatment will be assessed until recovery to Grade ≤ 1 or baseline, deemed irreversible, or until end of study. Adverse events leading to discontinuation will be followed up until resolution or return to baseline, or end of study, whichever occur first.

The primary analysis of the study will be performed 6 months after the last subject has received the first dose of study medication, or earlier if that subject discontinues study therapy. After the cutoff for primary analysis, subjects who are receiving study treatment can continue treatment per protocol until progression, unacceptable toxicity, withdrawal of consent, or other reason as listed in Section 11.2. End of study is defined as the last subject who completed the End of Treatment assessment. After the clinical cutoff at a minimum following data will be collected on eCRF: SAEs and AEs Grade ≥ 3 , laboratory assessments (Grade ≥ 3 or clinically significant), efficacy, survival status, and treatment administration. Data collected from the primary analysis until end of study will be summarized in a clinical study report addendum.

SUBJECT POPULATION

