| 
Treatment Period begins with the first administration of study therapy. EOT visit is required for all subjects and should take place within 30 days after last dose of study therapy with a window of ±7 days. If the subject requires subsequent anti-lymphoma/neoplastic therapy in the interim period between last dose of study drug and the EOT visit, then this visit should be completed just prior to initiation of subsequent therapy. Follow-up visits in all subjects will be completed every 3 months with a window of ±7 days until death or end of study. Note that the first FU visit should be approximately 100 days after end of nivolumab therapy; during this first FU visit, additional sampling will be done.
 
After the clinical cutoff, subjects who are ongoing on treatment continue all assessment per protocol, however data collected on eCRF will be limited to at least: SAEs and AEs Grade ≥3, laboratory assessments (Grade ≥3 or clinically significant), efficacy assessments, survival status, and study treatment administration.
 
Per Amendment 7, subjects who are receiving study treatment will continue all assessments per protocol. Data collected in the eCRF will be further limited to: SAEs and Grade ≥3 AEs that are at least possibly related to treatment, AEs leading to discontinuation or modification, efficacy assessments, and study treatment administration.
 | | | | | | |
| Weight/Height | Height at Screening only. | X | X | X | X | |
| 12-lead ECG | Assessment of triplicate ECG to determine QTcF; repeat ECG 3 times approximately 1-2 minutes apart. Predose Baseline= prior to any study treatment Predose C2D1=within 1 hour prior to nivolumab dosing | X | •Predose •Immediately after nivolumab infusion on C1D1 •2 hours after ibrutinib dosing on C1D1 | •Cycle 2 Day1: predose •Cycle 5 Day 1: after end of nivolumab infusion •To be repeated as clinically indicated | X | |
| Concomitant Medications | Collect up to EOT (within 30 days after the last dose of ibrutinib or whichever treatment occurred last). Thereafter, collect only subsequent anti-lymphoma/neoplastic therapy. | <-----X-----> | | | | |
| Adverse Events | Record all AEs from signing of ICF to EOT (within 30 days after the last dose of ibrutinib or nivolumab, whichever treatment occurred last). | <-----X-----> | | | | |
| Laboratory Assessments | | | | | | |

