3. STUDY DESIGN AND RATIONALE

3.1. Overview of Study Design

This is an open-label Phase 1/2a study, which consists of Part A (Dose Optimization Cohorts) and Part B (Expansion Cohorts). In the context of this study, a treatment ‘cycle’ is defined as a course of treatment of 14 days starting with the intravenous administration of nivolumab on Day 1 of each cycle along with once daily oral intake of ibrutinib on all days.

It is anticipated that approximately 158 subjects will be enrolled throughout the study; up to 18 subjects in the dose optimization period (Part A) and approximately 140 subjects during the expansion period (Part B).

Figure 1: Study Design Overview

Part A (Dose Optimization Cohorts) is designed to determine the RP2D for the combination based on safety, pharmacokinetic, and pharmacodynamic assessments. Two dose optimization cohorts will be explored, applying the Modified Toxicity Probability Interval (mTPI) design to evaluate subjects with relapsed/refractory CLL/SLL or B-NHL.

Part B (Dose Expansion Cohorts) will be open for enrollment after the RP2D is determined in Part A. In Part B, further assessment of the RP2D will be explored in 3 subject populations to further evaluate the safety and clinical activity of ibrutinib in combination with nivolumab. During the expansion period, subjects with CLL/SLL with del 17p or 11q (Cohort B1), FL (Cohort B2), DLBCL (Cohort B3), and Richter syndrome (Cohort B4) will be enrolled. Approximately 35 subjects will be enrolled in each of the expansion cohorts. The subjects will be treated at the RP2D level selected to further assess the safety, pharmacokinetics, pharmacodynamics, pharmacogenomics, and activity of the combination.

Part A and Part B of the study will be divided into 3 periods:

- Screening Period: pretreatment screening period of up to 28 days before enrollment
- Treatment Period: open-label treatment period ending at the End-of-Treatment Visit
- Follow-up Period: posttreatment follow-up period until the end of study (when all subjects have completed the End-of-Treatment Visit). Refer to [Table 1](#) for a complete list of procedures to be performed during the study.

During the Treatment Period, all subjects will be closely monitored for safety. Toxicities (AEs and laboratory abnormalities) will be evaluated and graded according to the National Cancer Institute Common Terminology Criteria for Adverse Events (NCI CTCAE Version 4).

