- subject refuses further therapy
- investigator's decision to withdraw the subject
- pregnancy of the subject
- noncompliance with study treatment or procedure requirements

The average duration of study therapy is expected to be approximately 6 months.

In Part A of the study, a SET, consisting of the principal investigators, sponsor medical monitors, and the sponsor's clinical pharmacologist, or their designees, and the sponsor statistician will review all available data upon completion of the first 2 treatment cycles (ie, 4 weeks of study therapy) for all subjects at each dose cohort to determine DLTs, if dose escalation is acceptable, and ultimately to determine the recommended Phase 2 dose.

In Part B of the study, all subjects in each cohort may be evaluated for response by the SET and additional functional representatives from Janssen, as applicable. The SET along with optional other internal members may review safety on an ad hoc basis, and efficacy endpoints (including but not limited to ORR).

The End-of-Treatment Visit will occur within 30 days after the last dose of ibrutinib or nivolumab, whichever treatment occurred last.

During the Follow-up Period, long-term safety, survival status, disease progression, subsequent anticancer therapy, and occurrence of other primary malignancy data will be collected as well as anti-drug antibody (ADA) sampling if applicable. During the Follow-up Period, subjects should be followed for safety up to 30 days after the last dose of ibrutinib or 100 days after the last nivolumab infusion, whichever is later. The safety follow-up includes adverse event reporting and laboratory assessments (at the first follow-up). Thereafter, follow-up visits will be completed approximately every 3 months until death or the end of study. Subjects who have developed treatment-related Grade 3 or higher toxicity at the end of treatment will be assessed until recovery to Grade ≤ 1 or baseline, deemed irreversible, or until end of study. Adverse events leading to

discontinuation will be followed up until resolution or return to baseline, or end of study, whichever occur first.

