The primary analysis of the study will be performed 6 months after the last subject has received the first dose of study medication, or earlier if that subject discontinues study therapy. After the cutoff for primary analysis, subjects who are receiving study treatment can continue treatment per protocol until progression, unacceptable toxicity, withdrawal of consent, or other reason as listed in Section 11.2. End of study is defined as the last subject who completed the EOT Treatment assessment.

After the clinical cutoff at a minimum the following data will be collected on eCRF: SAEs and AEs Grade ≥ 3 , laboratory assessments (Grade ≥ 3 or clinically significant), efficacy, survival status, and treatment administration. Data collected from the primary analysis until end of study will be summarized in a clinical study report addendum.

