18.9. Study Completion/Termination

18.9.1. Study Completion

The study is considered completed with the last visit for the last subject participating in the study. The final data from the study site will be sent to the sponsor (or designee) after completion of the final subject visit at that study site, in the time frame specified in the Clinical Trial Agreement.

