The primary analysis of the study will be performed 6 months after the last subject has received the first dose of study medication, or earlier if that subject discontinues study therapy. After the cut off for primary analysis, subjects who are receiving study treatment can continue treatment per protocol until progression, unacceptable toxicity, withdrawal of consent, or other reason as listed in protocol Section 11.2. End of study will be defined as the time when all subjects have completed the End-of-Treatment Visit and have been followed for safety up to 100 days post nivolumab as the last study assessment.

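### The protocol's end-of-study definition can close the study before the 100-day post-nivolumab safety follow-up is complete for the last subjects, and it differs from the SAP's definition

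*Protocol*

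**What the plan says.** **End of study in the protocol.** Section 3.1 gives "End of study is defined as the last subject who completed the EOT Treatment assessment", and the Synopsis gives "End of study is defined as the last subject who completed the End of Treatment assessment". The list of study periods in Section 3.1 ties the Follow-up Period to the same event: "posttreatment follow-up period until the end of study (when all subjects have completed the End-of-Treatment Visit".

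**Timing of the EOT visit.** Section 3.1: "The End-of-Treatment Visit will occur within 30 days after the last dose of ibrutinib or nivolumab, whichever treatment occurred last". Table 1 adds that it "should take place within 30 days after last dose of study therapy with a window of ±7 days".

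**Required safety follow-up.** Section 3.1 and the Synopsis state that "subjects should be followed for safety up to 30 days after the last dose of ibrutinib or 100 days after the last nivolumab infusion", taking the later of the two. Section 13.3.1 sets the same period for adverse event reporting. Table 1 places the first follow-up visit at about 100 days after nivolumab ends, with serum chemistry. The adverse event row of Table 1, however, records events only up to EOT.

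**End of study elsewhere.** SAP 1.2 requires that all subjects have completed EOT and "have been followed for safety up to 100 days post nivolumab as the last study assessment". Protocol Section 18.9.1 says "The study is considered completed with the last visit for the last subject participating in the study". SAP 2.2 runs the follow-up phase to the last assessment of the last subject.

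**The concern.** The protocol gives two rules for the same stretch of time. One closes the study, and the Follow-up Period with it, at the last EOT visit. The other requires safety observation for weeks beyond that visit in anyone recently infused. A site or data manager cannot tell from the protocol which rule governs closure, and the SAP follows only one of them.

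At stake is the completeness of late safety data. The SAP builds three windows on the 100 days: treatment-emergent adverse events (5.1), deaths (5.4) and laboratory data (5.5). If the study closes at the last EOT visit, these windows are only partly observed for the last subjects, and missing observation can only lower the count of late events.

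The protocol's own pharmacokinetics show that the interval is not empty of exposure. Section 3.2 gives a mean terminal half-life of 17 to 25 days. On simple exponential decline (an assumption), the fraction remaining at day 30 is 0.5^(30/17) = 0.29 to 0.5^(30/25) = 0.44. At day 100 it is 0.5^(100/17) = 0.02 to 0.5^(100/25) = 0.06.

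**Working it through.** No sample size, power or alpha figure bears on this point, so there is no stated figure to reproduce. The check is day arithmetic.

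**Inputs**
- Required safety follow-up: 100 days after the last nivolumab infusion, when later than 30 days after ibrutinib (Protocol 3.1, 13.3.1).
- EOT visit: by day 30 after the last dose of either drug (3.1), or day 37 with the +7-day window (Table 1).
- Cycle: 14 days, nivolumab on Day 1, ibrutinib daily (3.1). The last ibrutinib dose of a completed cycle is therefore 14 − 1 = 13 days after the infusion.
- Ibrutinib alone after nivolumab: possible after consultation with the sponsor; after Amendment 7, only for subjects scheduled to roll over to the extension study (6.4).

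**Formula.** Let k be the number of days from the last infusion to the last ibrutinib dose. EOT falls on day k + 30 (or k + 37), counted from the infusion. Shortfall for the last subject = 100 − (k + 30), or 100 − (k + 37), and not below zero.

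| Last subject | k | EOT day | Shortfall (days) |
|---|---|---|---|
| Both drugs stop on the infusion day | 0 | 30 to 37 | 100 − 30 = 70 to 100 − 37 = 63 |
| Ibrutinib taken to the end of the cycle | 13 | 43 to 50 | 100 − 43 = 57 to 100 − 50 = 50 |
| Ibrutinib alone continues | at least 70 (63 with the window) | at least 100 | 0 |

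The table takes EOT at day 30 or 37 after the last dose. The rule is within 30 days, so an earlier visit lengthens the gap: with both drugs stopped together and EOT on day 14, it is 100 − 14 = 86 days.

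**Other subjects.** Anyone whose last infusion was d days before the last subject's EOT visit, with d below 100, loses 100 − d days. The documents do not say how many subjects this would be.

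**Under the SAP 1.2 definition** the shortfall is zero. For a last subject who stops both drugs together, closure moves from day 30 (or 37) to day 100, which is 70 (or 63) days later; 70/7 = 10 weeks.

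**Does Amendment 7 remove the conflict?** Footnote a to Table 1 drops survival follow-up and lets subjects already in follow-up complete end-of-study assessments. It does not withdraw the 100-day safety period in the Synopsis, 3.1 or 13.3.1.

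**The case against.** The strongest reply is that the 100-day duty is also stated subject by subject. Section 13.3.1 carries it without an end-of-study limit, Table 1 schedules a visit for it, and in Section 3.1 the end-of-study limit on visits applies to those after the 100 days. A site following 13.3.1 would keep reporting. This shows what was probably intended, and it means that loss of data is not certain. It does not remove the conflict, because Section 3.1 also ends the Follow-up Period itself at the last EOT visit.

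Several stronger inferences are tempting, and the documents do not support them:

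- **That at least 63 to 70 days are always lost.** This assumes both drugs stop on the infusion day. The gap is shorter if ibrutinib continues, and can be nil.
- **That follow-up of unresolved toxicity stops at closure.** Section 3.1 does limit follow-up of treatment-related Grade 3 or higher toxicity to end of study. But Section 10.6 carries clinically significant abnormalities past that point, and 13.3.2 does so for unresolved serious events. The passages conflict; they do not add up to a stop. Nor do those two sections provide for detecting new events after closure.
- **That subjects remaining after Amendment 7 are mainly on the combination.** Neither document gives a count.
- **That the trial's safety conclusions are biased to a material degree.** Amendment 7 states that primary and secondary objectives had already been analyzed. Data after the clinical cutoff go to an addendum, and their collection is already narrowed. SAP 5.1 also counts a treatment-related event whatever its start date, provided it is reported.
- **That Section 18.9.1 is a third, incompatible definition.** The visit at about 100 days is a scheduled visit, so the last visit of the last subject is compatible with SAP 1.2.

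**Conclusion.** The point holds as an internal contradiction in current protocol text and a mismatch with the SAP. Followed as written, the end-of-study definition can close the study 63 to 70 days before the required safety follow-up ends for a last subject who stops both drugs on an infusion day, and 50 to 57 days before if ibrutinib runs to the end of the cycle. There is no gap if ibrutinib alone continues for a further 63 to 70 days or more. These figures assume that the last EOT visit takes place at day 30 to 37 after the last dose.

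The consequence is incomplete 100-day windows for adverse events, deaths and laboratory data in the last subjects, reported in the addendum. The primary analysis of response, timed at 6 months after the last subject's first dose or earlier if that subject discontinues, is unaffected. The size of any effect on a reported rate cannot be calculated, because the number of affected subjects is not given. This should be corrected, but it does not threaten the main result.

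**What to change.** 1. Reconcile the end-of-study wording in the Synopsis and in both places in Section 3.1 (the Follow-up Period entry and the definition itself) with SAP 1.2, so that end of study does not precede completion of the safety follow-up the protocol already requires: the later of 30 days after ibrutinib or 100 days after nivolumab. SAP 1.2 names only the nivolumab period besides EOT, so the same later-of wording should be carried into it.
2. Reconcile the adverse event row of Table 1, which stops at EOT, with Section 13.3.1. Otherwise the 100-day period stays contradictory for every subject, not just the last ones.
3. Reconcile the end-of-study limit on toxicity follow-up in Section 3.1 with Sections 10.6 and 13.3.2.
4. Leave Section 18.9.1 as it is, with a cross-reference to the agreed definition.

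The cost is amendment wording and study closure up to about 10 weeks later, taking EOT at day 30. No procedure is added beyond the follow-up already required.

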3.2. Study Design Rationale

Rationale for Ibrutinib Dose and Regimen Selection

The recommended monotherapy dose and schedule for ibrutinib is:

- CLL/SLL: 420 mg given orally per day
- B-cell malignancies including follicular lymphoma and Richter syndrome: 560 mg given orally per day

The starting dose of ibrutinib will be the recommended monotherapy dose for CLL (420 mg). Given that the mechanism of action of ibrutinib and nivolumab are distinct, as well as the fact that both compounds have very favorable safety profiles, combination treatment with both compounds together is not expected to result in additive toxicity.

In Part A, cohorts of 420 mg/day and 560 mg/day of ibrutinib will be explored as outlined in Section 6. Upon recommendation of the SET and in agreement with the study sponsor, additional dose cohorts and alternative dosing schedules may be explored. However, the starting dose of ibrutinib will not be increased above 560 mg/day or decreased below 420 mg/day.

Rationale for Nivolumab Dose and Regimen Selection

Single-dose pharmacokinetics (PK) of nivolumab were evaluated in 39 subjects with multiple tumor types in study MDX1106-01 in the dose range of 0.3 to 10 mg/kg. The median T_{max} across single doses ranged from 1.6 to 3 hours with individual values ranging from 0.9 to 7 hours. The PK of nivolumab is linear in the range of 0.3 to 10 mg/kg with dose proportional increase in C_{max} and $AUC_{(inf)}$ with low to moderate inter-subject variability observed at each dose level (ie, coefficient of variation (CV) ranging from 7 to 45%). Geometric mean clearance (CL) after a single intravenous (IV) dose ranged from 0.13 to 0.19 mL/h/kg, while mean volume of distribution (V_z) varied between 83 to 113 mL/kg across doses. The mean terminal t_{half} of nivolumab is 17 to 25 days, which is consistent with the half-life of endogenous IgG4, indicating that the elimination

mechanism of nivolumab may be similar to IgG4. Both elimination and distribution of nivolumab appear to be independent of dose in the dose range studied.

A preliminary population PK model was developed by nonlinear mixed effect modeling using data from 350 subjects from MDX1106-01, MDX1106-02 and CA209003. The body weight normalized dosing produces approximately constant trough concentrations over a wide range of body weight, and hence is appropriate for future clinical trials of nivolumab. Clearance of nivolumab is similar in all tumor types studied and is independent of dose range studied (0.1 to 10 mg/kg).

The dose and schedule selected for evaluation in this study, 3 mg/kg every 2 weeks, has been evaluated in solid tumors in the ongoing CA209003 study. Nivolumab was adequately tolerated up to 10 mg/kg, the highest dose level tested, and no MTD was identified. Anti-tumor activity was observed at dose levels ranging from 1 to 10 mg/kg in melanoma, NSCLC, and RCC, as well as at dose levels of 0.1 and 0.3 mg/kg in melanoma. The antitumor activity of nivolumab tended to increase with dose, as did the incidence of SAEs. The anti-tumor activity of nivolumab in RCC was investigated at dose levels of 1 and 10 mg/kg, with the higher activity observed at 10 mg/kg. The observed anti-tumor activity in melanoma, and NSCLC was highest at 3 mg/kg, suggesting that anti-tumor activity approaches a plateau at dose levels of 3 mg/kg and above. The ongoing CA209039 study in hematologic malignancies includes 2 dose levels: 1 mg/kg and 3 mg/kg every 2 weeks. The 3 mg/kg dose level has been shown to be adequately tolerable and this dose has been expanded in select tumor types for further evaluation. Objective responses have been observed at both dose levels in study CA209039. Based upon the totality of available data across the program, a dose of 3 mg/kg every 2 weeks is selected as the dose anticipated to maximize the benefit-risk ratio.

Refer to the current BMS-936558 (nivolumab) Investigator Brochure for additional information.

Rationale for Subject Population

In this study patients will be enrolled (1) whose tumor is amenable to therapy with either ibrutinib and/or nivolumab based on efficacy data generated in previous studies but (2) who are in need of effective therapies. This includes patients with CLL/SLL whose disease presents with the recurrent chromosomal abnormalities del 17p or del 11q which are associated with rapid progression, poor response to chemotherapy, and shorter survival. Similarly, the particular populations of patients with relapsed and/or refractory FL, DLBCL or Richter syndrome selected for this study are in need of additional effective therapeutic options.

Rationale for Pharmacokinetic Analysis

Pharmacokinetics of ibrutinib and nivolumab when administered in combination will be evaluated in this study as specified in [Table 2](#).

Rationale for Anti-Nivolumab Antibodies

The emergence of antibodies against nivolumab has been low, but as this is a new combination treatment regimen the development of anti-drug antibodies will be monitored. Anti-nivolumab antibodies will be evaluated in the study as specified in [Table 2](#).

Rationale for Pharmacodynamic and Biomarker Analysis

This study is based on the hypothesis that the combination of these 2 drugs will potentiate each other, and therefore the biomarker and pharmacodynamics evaluations are important in understanding the mechanism of action of the combination. Biomarker sampling during the course of the study will help to examine changes in the immune system and in the tumor. Fine needle aspirates from lymph nodes will be collected at baseline and at C3D1 in selected cohorts, in order to examine the possible changes in the T-cell subtypes within the tumor microenvironment, as these may differ from the peripheral blood compartment. Tumor biopsies obtained at screening and post-progression may contribute to understanding the mechanism of resistance to drug treatment and may aid in the development of biomarkers to identify subjects in need of additional or modified therapy.

Peripheral blood and tumor tissue will be collected prior to therapy and at selected timepoints on treatment as outlined in [Table 1](#) and [Table 2](#) unless restricted by local requirements.

